5.2 Primary Endpoint: Incidence of MMID

MMID is defined as positive if a participant has both detectable shedding, as evaluated by RT-qPCR (reverse transcriptase quantitative polymerase chain reaction), and at least one symptom,

as observed on the Physician Assessment of Influenza Symptoms (PAI), at any time during subject quarantine, starting from the evening of Day 1 post-inoculation through the expected end of the quarantine period, Day 7, Discharge. The analysis of this endpoint will be performed by comparing the MMID rates in each of the FLU-v groups to the placebo group. Comparisons will be performed using one-sided Fisher's exact test, and the proportion of subjects with MMID and corresponding p-value will be presented. If a subject has no nasal swab data on two consecutive days, and the available recorded data shows no shedding, the MMID for that subject will be considered as missing. Similarly, if symptom data is not recorded on two consecutive days, and the available recorded data shows no symptoms, the MMID will be considered as missing for that subject. However, if a subject is positive for viral shedding and experiences at least one symptom with the available recorded data, that subject will be included in the MMID analysis. The primary analysis will incorporate missing data as described in section 5.7. The statistical summary data will be presented as tables and figures as described in sections 8-9 of this document.

5.3 Secondary Objectives:

To determine the overall effect of FLU-v on influenza disease based on disease severity measures (presence or absence of symptoms or shedding, symptom severity, symptom and shedding duration, total symptoms and shedding, and peak symptom and shedding). Viral shedding was evaluated by RT-qPCR and symptoms were evaluated by PAI, from the evening of Day 1 post-inoculation (more than 24 hours after inoculation) through the expected end of the quarantine period (Day 7, Discharge).

5.4 Secondary Endpoints:

- Overview of symptoms (PAI) and of viral shedding (RT-qPCR) from the evening of Day 1 post-inoculation (more than 24 hours after inoculation) through Day 7.

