 - If a subject has no nasal swab data on two consecutive days, and the available recorded data shows no shedding, the endpoint will be considered as missing. Similarly, if symptom data is not recorded on two consecutive days, and the available recorded data shows no symptoms, the endpoint will be considered as missing for that subject. However, if a subject is positive for viral shedding with the available recorded data, that subject will be included in the analysis. Similarly, if the subject shows at least one symptom within the recorded data, that subject will be included in the analysis.

- Modified MMID
 - Incidence of at least two symptoms (on PAI) and viral shedding (RT-qPCR) at any time during the quarantine from evening of Day 1 post-inoculation through Day 7. If a subject has no nasal swab data on two consecutive days, and the available recorded data shows no shedding, the Modified MMID will be considered as missing. Similarly, if symptom data is not recorded on two consecutive days and the available recorded data shows no symptoms this endpoint will be considered as missing for that subject. However, if a subject is positive for viral shedding and experiences at least two symptoms with the available recorded data, that subject will be included in the modified MMID analysis.
- Viral shedding duration (days)
 - Measured from the first day with a positive test on RT-qPCR, starting from evening of Day 1 post-inoculation until the last day with a positive test during the expected quarantine period (up to Day 7). Intervening negative or missing test days will be included in the duration. If no positive test occurs, duration is counted as zero.
- Viral shedding quantitation (RT-qPCR)

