 - Area under the curve (AUC) will be calculated based on each timepoint tested on RT-qPCR (log copy number/ml) record from evening of Day 1 post-inoculation to the morning of Day 7 (last timepoint before expected quarantine discharge) using Trapezoidal rule, and those samples below lower limit of quantification (LLOQ) will be replaced by half of LLOQ. Linear interpolation will be used for a single missing measurement. If more than one consecutive point is missing, the endpoint is considered as missing. RT-qPCR peak during entire quarantine period (i.e. the highest level of RT-qPCR recorded anytime during the quarantine period, starting from evening of Day 1 post-inoculation up to Day 7. A single maximum RT-qPCR (peak) will be identified for each subject during the quarantine on the assumption that a peak is recorded during the quarantine. Thus, there will not be imputation to predict the peak for subjects who have suspected missing peak data as it is implausible to predict the missing peak from the rest of the existing data.
- Symptom duration in days (PAI)
 - Number of days from first symptom noted, starting the evening of Day 1 post-inoculation until the day of last symptom noted up to Day 7. Intervening days with no symptoms or

missing symptom data will be included in the duration. If no symptoms occur during the entire period, number of days is zero.

- Total number of symptoms experienced (PAI)
 - Mean of total number of symptoms (upper and lower respiratory and systemic symptoms) experienced from the evening of Day 1 post-inoculation until the day of last symptom noted during the expected quarantine period (up to Day 7). Calculated as the total sum of symptoms experienced divided by the number of days in which symptoms were collected.
- Total symptoms score peak (PAI)
 - The highest level of the total sum of all upper and lower respiratory tract and systemic symptoms recorded on any day starting from the evening of Day 1 post-inoculation until the day of last symptom noted during the expected quarantine period (up to Day 7).
- Symptom severity score as measured by FLU-PRO Symptom Questionnaire
 - Mean of daily score over all study quarantine days from Day 1 post-inoculation to Day 7. If a day has missing data, this day will be excluded from the mean calculation (days with 0 as the symptom severity will be included in calculating the average).

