- Comparison of each treatment group to placebo of the proportion of asymptomatic infected subjects defined as subjects with symptom score of zero (PAI) from Day 1 post-inoculation time-point through the expected end of quarantine (Day 7) with at least one positive result for viral shedding (RT-qPCR) in any of the quarantine days from the evening of Day 1 post-inoculation.
- Summary of Adverse Events from the Post-Vaccination Diary Card
 - The number of subjects who self-reported at least once any of the adverse events listed in the Post-Vaccination Diary Card during the 21 days following first vaccination and 21 days following second vaccination. Data will be presented for each treatment group by event and according to severity (mild, moderate, severe). The number of subjects in each treatment group with no self-reported events will also be presented.

The statistical software to be used for the analyses will be SAS (version 9.4) and R (version 3.43). The analyses of the secondary binary endpoints will be performed by comparing the rates in each of the FLU-v groups to the placebo group using one-sided Fisher's exact test. For all secondary endpoints, the primary analysis will assume missing data is missing at random so missing data will be ignored.

The analysis of all continuous secondary endpoints will be performed by calculating the median and interquartile range and then performing a one-sided Wilcoxon Rank Sum Test at 0.05 level of significance. These data will be reported as tables and figures as described in sections 8-9 of this document.

Statistical analysis will be performed by a junior statistician at NIAID-NIH and will be reviewed by the senior statistician. In addition, the Senior Clinical and Scientific Leader, will repeat the statistical analysis to validate the results.

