5.7.3 Binary endpoints

- Primary analysis: Assuming missing data is missing at random: ignore missing data
- Sensitivity analysis: impute the placebo group's proportion of events for the missing data in each group
- Sensitivity analysis: for placebo group impute observed proportion from vaccine group and for vaccine group impute observed proportion from placebo group

5.7.4 Continuous endpoints:

- Primary Analysis: ignore missing data
- Sensitivity analysis: In Wilcoxon test give placebo group the best rank and the vaccine group the worst rank

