- a) box plots with medians, 25%, 75%tiles by group will be shown ignoring missing data.
- b) box plots with medians, 25%, 75%tiles by group will be shown imputing missing as described for the sensitivity analysis.

Figure	Title
14.1.1	Subject Disposition – Safety
14.2.2.1	Viral Shedding Duration (days) – Intent to Treat
14.2.2.2	Viral Shedding AUC – Intent to Treat
14.2.2.3	Viral Shedding Peak – Intent to Treat
14.2.2.4	Symptom Duration (days) – Intent to Treat
14.2.2.5	Average Number of Symptoms – Intent to Treat
14.2.2.6	Total Symptom Score Peak – Intent to Treat
14.2.2.7	Symptom Severity Score (FluPRO) – Intent to Treat

9 Appendix – Shell Figure 14.1.1 and Shell Tables

Shell tables are provided as a separate document

Figure 14.1.1

DC = Discharge; WD = Withdrawal; FU = Follow-up

Source dataset:

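### Viral shedding duration is scored zero when no positive swab was recorded, however little was observed, so a subject who is missing for MMID can receive the best possible duration

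*SAP*

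**What the plan says.** **Shedding duration (SAP 5.4).** Duration runs from the first to the last positive RT-qPCR day, from the evening of Day 1 up to Day 7. Gaps are covered only when they lie between positive days: "Intervening negative or missing test days will be included in the duration". Where nothing positive was found: "If no positive test occurs, duration is counted as zero".

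**Symptom duration (SAP 5.4).** This is built the same way from the physician assessment (PAI): "If no symptoms occur during the entire period, number of days is zero".

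**Asymptomatic infected (SAP 5.4).** The endpoint is the "proportion of asymptomatic infected subjects defined as subjects with symptom score of zero (PAI") from Day 1 through Day 7 among those with at least one positive swab. No missing-data rule is attached.

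**Other endpoints from the same records.** For MMID (SAP 5.2), if swabs are absent on two consecutive days "and the available recorded data shows no shedding, the MMID for that subject will be considered as missing". For symptoms, "if symptom data is not recorded on two consecutive days, and the available recorded data shows no symptoms, the MMID will be considered as missing". The overview endpoint and Modified MMID repeat this rule, and keep in the analysis subjects who are positive on the data available. Shedding AUC is missing when more than one consecutive timepoint is missing.

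**Handling once missing.** SAP 5.7 acts on data that are missing as section 5 defines it. For continuous endpoints, 5.7.4 ignores missing values in the main analysis and adds a sensitivity analysis: "In Wilcoxon test give placebo group the best rank and the vaccine group the worst rank". The Summary of Figures in SAP 8 asks for every box plot twice, once ignoring missing data and once in a version that "will be shown imputing missing as described for the sensitivity analysis".

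**The concern.** Several endpoints derived from the same swabs treat the same gap in opposite ways. For MMID, Modified MMID, the overview and AUC, not having looked means not known. For shedding duration, not having looked means zero days, the best value on a 0 to 7 day scale.

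The zero counts as an observed value, so nothing in 5.7 catches it. Section 5 never defines a duration as missing. The worst-rank analysis therefore has nothing to act on for shedding duration, and the two versions of that box plot would be identical.

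At stake is a one-sided comparison of a secondary severity endpoint. If incomplete observation after challenge differs between arms, the arm with more of it gains an advantage, and the planned check cannot reveal it.

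**Working it through.** **1. The plan's own figure.** The documents give no sample size or power for the duration endpoints. The SAP's 40 per arm for MMID 0.70 versus 0.40 (one-sided 0.05, 80% power) reproduces with the continuity-corrected two-proportion formula, which gives 40 (33 without the correction). It does not bear on this point. The illustration below uses the protocol's 41 per arm.

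**2. The rules applied to one record.** A challenged subject has no swabs on Days 3 and 4, and every other swab is negative.

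| Endpoint | Result | Next step under SAP 5.7 |
|---|---|---|
| MMID | missing | placebo proportion imputed (5.7.1) |
| Modified MMID | missing | 5.7.3 |
| Shedding overview | missing | 5.7.3 |
| Shedding AUC | missing | 5.7.4 |
| Shedding duration | **0 days** | none; counted as observed |

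Now take a shedder with two consecutive unrecorded PAI days and no symptom on the others. MMID is missing. Symptom duration could be scored 0, and the subject could be counted as asymptomatic infected.

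If only one isolated day is unrecorded, MMID is not missing either, and there is no conflict.

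**3. How often a gap hides a whole episode.** The documents give no duration distribution or missing-data rate, so these are assumptions: 70% shed; durations are 1 to 7 days with equal probability; shedding is continuous; onset is uniform over the days that fit within Days 1–7.

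- *Random two-day gap (six positions).* A one-day episode is hidden with probability 12/42 = 2/7, a two-day episode with 1/6, a longer one never. Average: (2/7 + 1/6)/7 = 19/294 = 6.5% of shedders.
- *Drop-out after Day 1, 2, 3, 4 or 5 (equally likely).* For durations 1 to 7 the hidden probabilities are 20/35, 15/30, 10/25, 6/20, 3/15, 1/10 and 0. Average: 2.071/7 = 29.6% of shedders.

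With k = 4 affected subjects, the expected number of false zeros is 4 × 0.70 × 0.065 = 0.18 for gaps and 4 × 0.70 × 0.296 = 0.83 for drop-out.

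**4. Effect on the one-sided Wilcoxon test.** Simulation with 41 per arm, no true effect, nominal 5%, the distribution above, and all k affected subjects in one FLU-v arm. Ranges are across separate runs. With 8,000 replicates the Monte Carlo error is about 0.25 points.

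| Scenario | k=1 | k=2 | k=4 |
|---|---|---|---|
| Random two-day gap | 4.6–5.1% | 5.0–5.7% | 5.7% |
| Permanent drop-out | 5.7–6.1% | 6.3–6.7% | 8.8–9.0% |
| Every affected subject forced to zero (upper bound) | 6.0–6.6% | 7.6–8.3% | 12.6–13.1% |

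With k = 0 the rate is 4.9%. If all affected subjects are instead left out, it stays at 4.7–5.5%. If they receive the 5.7.4 worst rank, it falls to 2.7%, 1.8% and 0.3% for k = 1, 2 and 4. With equal numbers per arm forced to zero there is no inflation: 4.7% at 2+2 and 4.0% at 4+4.

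The first two rows also include episodes that were partly seen and so shortened. Not all of that excess comes from the zero rule.

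**The case against.** The strongest reply is that the exposure is small. Subjects live in isolation, are swabbed twice a day and are assessed daily by a physician. Early withdrawal is strongly discouraged (protocol 7.4.1). SAP 5.7 expects little missing data, and the SAP 8 table footnote puts the per-protocol and ITT sets one subject apart. The protocol (9.3.3) expects 3 to 5 days of shedding, and a continuous episode of that length cannot be hidden by a two-day gap. These are secondary endpoints, and the primary endpoint has its own missing-data rule and sensitivity analyses. All of this stands as to size. It does not settle how an affected record is to be scored.

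The wording can also be defended in part. The symptom-duration sentence refers to the whole period. The asymptomatic-infected definition asks for a score of zero through Day 7, and an unrecorded score is not a zero. Both can be read as requiring full observation, so they are ambiguities. The shedding-duration sentence has no such words. The overview rule is a sub-bullet of its own endpoint and is restated for Modified MMID, so it does not clearly carry over to the durations.

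A reader might infer more than the documents support:

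- *That any unobserved day creates the conflict.* It needs at least two consecutive unrecorded days with nothing positive recorded.
- *That the SAP plainly expected missing durations.* Section 5.7.4 and the figure instruction cover all continuous endpoints, including AUC, which can be missing.
- *That the planned protection never runs.* It still runs for AUC from the same swabs.
- *That one subject reliably adds over 1.5 points of type I error.* That holds only if the subject is forced to zero whatever was seen.

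**Conclusion.** The point holds for shedding duration as written. An unobserved stretch with no recorded positive becomes 0 days, while MMID, Modified MMID, the overview and AUC treat it as missing, and the 5.7.4 sensitivity analysis cannot reach it. For symptom duration and asymptomatic infected, the text permits the same scoring but does not compel it.

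The bias has no built-in direction. It favours whichever arm has more affected subjects and is absent when numbers are equal. With all affected subjects on FLU-v and k from 1 to 4, one-sided type I error is about 5–6% for two-day gaps and about 6–9% for drop-out. The roughly 13% at k = 4 is an upper bound, not an expectation. These figures rest on the assumed share of shedders, duration distribution, onset and one-sided missingness. The SAP's expectation of little missing data makes a small k the likely case. The reason to act is that the inconsistency is real and the repair is nearly free.

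**What to change.** Add the rule already used for the overview endpoint to the shedding-duration bullet in SAP 5.4: if swabs are absent on two consecutive days and no positive is recorded, shedding duration is missing. Mirror it for PAI records in the symptom-duration and asymptomatic-infected bullets: if assessments are absent on two consecutive days and no symptom is recorded, the endpoint is missing. Sections 5.7.3 and 5.7.4 and the second set of box plots then apply without further change.

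Keep subjects with a recorded positive (or, for symptom duration, a recorded symptom) in the main duration analysis, as the SAP does now. Setting a known shedder to missing because later days are unrecorded would discard a known lower bound on duration. It would also go against the SAP's practice of including subjects who are positive on the data available.

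The cost is a few sentences and one programming condition. A few subjects may leave the main analysis of these endpoints. Shortened durations in partly observed shedders remain as they are. Incomplete records then stay in the duration analyses only when something positive was seen, which can make the arm with more gaps look slightly worse. Reporting the number of affected subjects by arm would let a reader judge whether any of this matters.

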9	A history of childhood asthma before the age of 12 years is acceptable provided the subject is asymptomatic without treatment. Subjects with a single episode of wheezing (lasting less than 2 weeks) after the age of 12 years can be included at the Investigator's discretion provided the episode was more than 1 year ago and did not require a hospital admission and/or oral/intravenous steroids.
10	In good health with no history of major medical conditions that will interfere with subject safety, as defined by medical history, physical examination, and routine laboratory tests and determined by the Investigator at a screening evaluation. 
• A subject with a history of Herpes type 1 or 2 infection may be included if there are no active lesions present and the subject is not taking active medication.• A subject with or without any evidence of atopy including any history of allergic rhinitis, dermatitis, and conjunctivitis will be included as long as they do not conflict with exclusion criteria. Mild to moderate arthritis of non-inflammatory origin may be allowed if the subject is not at risk from relative immobility in the Quarantine Unit and does not require regular medication.
11	A documented medical history for a minimum of the last 2 years prior to inoculation.

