8.4 Alcohol, caffeine and xanthine-containing food and beverages

Subjects should abstain from alcohol, caffeine and xanthine-containing food and beverages (e.g., coffee, tea, energy drinks, cola, chocolate) between 24 hours prior to vaccine and dosing as well as prior to admission to quarantine. They will continue to abstain until after discharge from quarantine unit. Decaffeinated drinks will be provided during the quarantine period.

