Visits	Visit 1	Visit 2	21 days post vaccination 1	Visit 3	21 days post vaccination 2	Visit 4								Visit 5	Visit 6		
Study Phase >	Screen	IMP DOSING		IMP DOSING		Quarantine Admission	Inpatient								Follow-Up	Follow-Up	
Study Day >	~ DAY -- 90 to - 43	D-43	D-22	D-2	D-1	D0	D1	D2	D3	D4	D5	D6	D7	D8 - 15	D35 (+/- 3 days)	D63 (+/- 5 days)	Or Early withdrawal visit
Biochem: Creatine Kinase, and Total Protein	X				X					X		X		(X) ²	(X) ²	(X) ²	
Serum / Whole Blood Collection ⁷	X				X	X		X		X		X		(X) ²	X	X	
HIV, Hepatitis A/B/C	X				X ⁵												

KEY NOTES FOR TIME AND EVENTS SCHEDULES

Symbol	Notes
	Results of tests or examinations performed under other ethically approved hVIVO protocols, and within 90 days prior to admission to quarantine, may be used to determine eligibility without the need to repeat the assessment at study specific screening.
*	If continued viral shedding is detected on Day 7, the participant(s) will remain in quarantine as an inpatient and will continue to have nasal swabs and physician assessment and exams. In addition FLU-PRO symptom questionnaires will continue up to day 15. Any other procedures will be performed if deemed necessary by the study physician.
†	Vital Signs and ECG's: participants must be supine for a minimum of 5 minutes prior to these procedures being performed; vital signs include blood pressure, mean blood pressure, heart rate, respiratory rate, temperature, pulse oximetry. During the quarantine confinement vital signs will be taken 3 times a day at the same time +/- 1 hour except on Day -2, when it will be conducted once and on discharge day when it will be performed once or twice depending on discharge time. ECG should be performed once daily
‡	Females only - Serum pregnancy testing at the screening visit and, urine pregnancy testing on Days -43, -22, -2, 35 and 63.
§	FLU-PRO Symptom Questionnaire(s) will be filled out daily in the evening on Days -2 or-1, 0 through to Day 15, and on Day 35
Δ	
 NP nasal sampling will take place 2 times a day at the same time +/- 1 hour, except on Day -2 / -1 where there is one baseline sampling and on discharge day. No nasal sampling will take place on Day 0. NPS - tolerance only at screening

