(X)	Optional - Only for subjects kept in VCU after D7. If the subject is not discharged on day 7, they will continue to have vital signs, physical assessments, nasal swabs, adverse events & concomitant medication check, and FLU-PRO questionnaires performed daily.
1	DPE to be performed before and after inoculation at D0
2	These assessments will be performed at the PI's discretion
3	Spirometry will be performed during the inpatient phase in presence of lower respiratory tract symptoms
4	A continued suitability check will be conducted by the physician to determine if subject is suitable to continue study participation
5	Repeat HIV test if screening results are more than 60 days prior to entry to Quarantine (on Day -2 or Day -1)
6	Assessments will be performed once, either on Day -2 or Day -1
7	Challenge virus Serology will be performed only at Screening visit. A repeat may be requested before admission if required, however, the serology test and result must be dated within 90 days of Day 0. PBMC & PAXgene samples will be collected from subjects, either at their screening visit or at a planned PBMC sampling visit prior to their vaccination.

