13.2 Efficacy assessments

Assessments to determine the efficacy of the IMP will be performed at the times detailed in T&E. Unless otherwise indicated, the value obtained at screening will be used as the baseline for efficacy assessments.

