16.6 FLU-v Secondary analysis

A secondary analysis will be performed to examine the secondary endpoints for this study. Adverse event rates between the three groups will be compared using Fishers exact test. The days of shedding, days of symptoms, number of symptoms, and FLU-PRO scores between will be examined by calculating the median and interquartile range for all three groups and then performing a two-sided Wilcoxon Rank Sum Test at the 0.05 significance level.

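### The FLU-PRO severity comparison leaves unused the pre-challenge FLU-PRO score already collected; the test is valid, and the cost is some precision of unknown and possibly small size

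*SAP*

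**What the plan says.** SAP 5.4 defines the FLU-PRO severity endpoint as "Mean of daily score over all study quarantine days from Day 1 post-inoculation to Day 7". Days with missing data are left out of the mean and days scoring zero are kept. Continuous secondary endpoints are summarised by median and interquartile range, "then performing a one-sided Wilcoxon Rank Sum Test at 0.05 level of significance". Neither the sensitivity analysis for continuous endpoints (SAP 5.7.4) nor the post-hoc FLU-PRO analysis (SAP 5.8) brings in a pre-challenge score.

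The key notes to protocol Table 9-2 say that FLU-PRO "will be filled out daily in the evening on Days -2 or-1, 0 through to Day 15, and on Day 35". For the admission assessment, note 6 adds: "Assessments will be performed once, either on Day -2 or Day -1". So there is one FLU-PRO score before Day 0, and none at screening or before the first vaccination.

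On baselines, protocol 13.2 says that "the value obtained at screening will be used as the baseline for efficacy assessments", subject to a proviso that another value may be specified. Protocol 13.1 uses pre-vaccination values for clinical assessments. Protocol 16.4 leaves the description of all baseline assessments to the SAP, and the SAP describes none for FLU-PRO.

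**The concern.** FLU-PRO (protocol Appendix 1) has 32 items, among them runny nose, congestion, sneezing, headache and tiredness. It asks how far each was present over the past 24 hours and does not ask about cause. The MMID definition in protocol 4.2 differs here, because the investigator must judge the symptom related to influenza. Background symptoms therefore go straight into the FLU-PRO score.

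Some background is plausible. Inclusion criterion 10 admits "A subject with or without any evidence of atopy including any history of allergic rhinitis", subject to the exclusion criteria. Criterion 7 restricts antihistamines and decongestants from 14 days before vaccination to final follow-up unless approved. A subject with mild untreated rhinitis could score above zero on every day of the stay for reasons unrelated to the challenge virus.

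Stable differences between people add variance to the Day 1-7 mean. A score taken from the same person just before challenge could remove part of it. At stake is some power on one secondary endpoint, together with a gap in the documents: the default baseline has no FLU-PRO value and no other is named.

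**Working it through.** **Inputs from the documents.** 41 subjects per arm (protocol 16.2); one-sided alpha 0.05 (SAP 4); 1:1:1 allocation; Wilcoxon test on the Day 1-7 mean (SAP 5.4); one pre-challenge FLU-PRO score (protocol Table 9-2).

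**Inputs that are assumed.** The correlation r between the pre-challenge score and the Day 1-7 mean, the starting power of 0.80, and the shape of the scores. The documents give none of these for FLU-PRO.

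**1. The plan's own figure.** For MMID at 0.70 versus 0.40, exact one-sided Fisher power is 81.3% with 41 per arm (protocol states 80%) and 79.8% with 40 per arm (SAP states 80%). Both reproduce. This sizing is for MMID, so 0.80 serves below only as a reference point.

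**2. Reference effect.** With 41 per arm, the standardised difference giving 80% power is (1.645 + 0.842) × √(2/41) = 0.549 for a t-type test. Dividing by √(3/π) = 0.977 for the Wilcoxon test gives 0.562.

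**3. Effect of adjustment.** Adjusting for a baseline with correlation r multiplies the residual variance by 1 − r². Power becomes Φ(2.487/√(1 − r²) − 1.645). For example, at r = 0.3 this is Φ(2.487/0.954 − 1.645) = Φ(0.962) = 0.832.

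| r | Variance removed | Power, adjusted | Power, plain change score |
|---|---|---|---|
| 0 | 0% | 0.800 | 0.545 |
| 0.1 | 1% | 0.803 | 0.583 |
| 0.2 | 4% | 0.814 | 0.626 |
| 0.3 | 9% | 0.832 | 0.676 |
| 0.4 | 16% | 0.857 | 0.734 |
| 0.5 | 25% | 0.890 | 0.800 |

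The last column replaces 1 − r² by 2 − 2r, which assumes equal SDs at baseline and afterwards. On that assumption a change score loses power whenever r is below 0.5. Starting from 0.80 power at two-sided 0.05, the adjusted column hardly changes (0.816 at r = 0.2, 0.899 at r = 0.5).

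**4. Scores with many zeros.** The formula is a normal-theory approximation, and healthy subjects may mostly score zero. A simulation (4,000 trials per setting, 41 per arm) gave a share of subjects zero background and the rest a skewed background score. A skewed illness score was added, with placebo mean 0.30 and vaccine mean 0.55 times that.

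| Zero background | Mean background in the rest | Wilcoxon | Rank ANCOVA | Gain (points) |
|---|---|---|---|---|
| 90% | 0.10 | 0.734 | 0.742 | 0.8 |
| 80% | 0.10 | 0.718 | 0.735 | 1.7 |
| 60% | 0.15 | 0.656 | 0.728 | 7.2 |
| 40% | 0.20 | 0.596 | 0.737 | 14.1 |
| 20% | 0.30 | 0.506 | 0.748 | 24.2 |

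With no vaccine effect, rejection rates for the Wilcoxon test, rank ANCOVA and a Wilcoxon test on change lay between 0.040 and 0.052 in every setting.

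Two cautions apply. The lower rows raise the background mean as well as its frequency. The background also carries into Days 1-7 unchanged and is measured at baseline with little error, which favours adjustment. For the same reason the change score did nearly as well as rank ANCOVA here (0.726 to 0.740 across the settings). That would not hold if one day's score were a noisy guide to the following week.

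**The case against.** The strongest reply is that nothing here is wrong. Protocol 16.6 names a Wilcoxon test, and the SAP uses one for every continuous secondary endpoint. The test is valid, the endpoint is not a change score, and so no baseline is needed to compute it. Subjects are healthy, the suitability check looks for acute illness within 7 days of admission, a respiratory virus screen is run at admission, and daily smokers are excluded. A history of rhinitis is not active rhinitis. All of this stands, and it is why the gain may be only a point or two. It does not remove the case for using a value already collected.

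Four stronger readings are tempting, and the documents do not support them.

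- A reader might infer bias, or an inflated chance of a false positive, from imbalance in background symptoms. Under randomisation the test's error rate already allows for chance imbalance.
- A reader might infer that the screening baseline in protocol 13.2 spoils the FLU-PRO result. It changes no FLU-PRO number, and its proviso lets the SAP name another value. The fault is only that the SAP does not.
- A reader might cite caffeine, of which protocol 8.4 says "They will continue to abstain until after discharge from quarantine unit", or the rule that casual smokers refrain during the stay. Caffeine stops 24 hours before admission and smoking only for the stay, so a single admission score with 24-hour recall largely reflects the period before or just as these changes begin. They are weak evidence of stable symptoms that the score would capture.
- A reader might extend the point to the physician symptom assessment. The argument here rests on self-report without attribution of cause and does not carry over.

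**Conclusion.** The point holds as a minor, optional gain in precision on one secondary endpoint. The SAP does not use the Day -2/-1 FLU-PRO score and names no FLU-PRO baseline, although protocol 16.4 left baselines to it. The planned comparison remains valid.

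The size is not known. It ranges from almost nothing, if r is near 0.1 or 80-90% of subjects score zero before challenge, to about 9 points of power at r = 0.5 from an assumed 0.80. The larger simulated gains need background symptoms in most subjects, or close to it, which the documents do not show.

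A separate matter needs its own resolution: the protocol specifies "performing a two-sided Wilcoxon Rank Sum Test at the 0.05 significance level" for this endpoint, while the SAP's test is one-sided. The present point does not depend on which is used.

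**What to change.** Before unblinding:

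- In SAP 5.4, define the FLU-PRO baseline as the single Day -2/-1 score. Day 0 is unsuitable: it is completed in the evening with 24-hour recall and may include hours after inoculation.
- Compare each FLU-v arm with placebo by rank analysis of covariance, with the rank of the Day 1-7 mean as outcome and the rank of the baseline as covariate. Do not use a plain change score, which can lose power when the correlation is modest.
- State a rule for a missing baseline, for example the pooled median rank, so that no subject is dropped.
- Report the protocol-specified unadjusted Wilcoxon test alongside.
- Record the departure in SAP section 6, which now declares no change to the protocol-specified analyses apart from the post-hoc ones.

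No new data are needed. The cost is a documented departure from the protocol's test and a few lines of code. If the data have already been unblinded, the adjusted analysis should be labelled post hoc.
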